4. Preoperative photograph will be taken.

Operative procedure:

Experimental group:

1. Injection of local anesthesia and rubber dam isolation.
2. Roof of the pulp chamber will be removed by a fissure diamond bur (Diatech, Heerbrug, Switzerland) and high-speed handpiece with coolant.
3. The pulps will be amputated to the orifice level using a long-shank diamond round bur.
4. Haemostasis will be achieved by gentle placement of a saline-moistened cotton pellet over amputated pulps for 5–10 min.
5. Calcium silicate-based Biodentine™ (Septodont Ltd., Saint Maur des Fausse's, France) will be mixed according to the manufacturer's instructions, radicular pulp will be covered by the material using a wet cotton pellet.
6. A self-cure glass ionomer (GC; GC Corporation, Tokyo, Japan) will be placed over the pulpotomy agent before final restoration of composite resin (Clearfil™, Kuraray, New York, USA) will be done.
7. Immediate post-operative radiograph and photograph will be taken.

Control group:

The same procedures will be carried out as the experimental group, but the pulp stumps will be covered with white mineral trioxide aggregate (MTA) ProRoot® MTA (Dentsply/ Johnson City, TN, USA) will be used as the reference material for comparison and will be prepared according to the manufacturer's instructions. A 3-mm-thick layer of MTA will be placed over the amputated pulps and will be gently adapted to the dentinal walls using a wet cotton pellet deep onto the radicular pulp. A self-cure glass ionomer (GC; GC Corporation, Tokyo, Japan) will be placed over the pulpotomy agent before final restoration of composite resin (Clearfil™, Kuraray, New York, USA) will be done.

Postoperative care:

Instructions to avoid lip biting in addition to oral hygiene measures.

Follow up:

Assess the outcomes clinically and radiographically at (baseline, 6, 12 and 18 months).

Criteria for discontinuing or modifying intervention:

In case of an unsuccessful outcome after pulpotomy, the teeth will be managed by other pulp therapy techniques.

Strategies to improve adherence to intervention:

Explanation to the parents about the importance of follow up visits in addition to treatment of other dental problems.

Concomitant care:

None needed.

12- Outcomes:

	Outcome	Tool/Device	Unit
Primary Outcome	spontaneous pain, sensitivity to percussion/ palpation)	Pain questionnaire	Binary
	Swelling or sinus tract	Visual examination by the third author	Binary
	Mobility	Back of the mirror	Binary

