Numbered opaque sealed envelopes.

Implementation:

The child will choose an envelope randomly and open it after access preparation so that the operator knows which pulpotomy agent will be used. Sequence generation will be done by the third author and the patient assignment will be done by the operator.

17- Blinding:

Patients and their parents, the assessor and the statistician will be blinded.

18- Data collection methods:

Primary outcome:

Clinical assessment of the following findings:

1. postoperative pain: through asking the child and the parent if there is pain

either continuous or intermittent

2. Swelling: through visual examination by the assessor either intraorally or extra-orally.
3. Sinus or fistula through visual examination of the gingiva by the assessor.
4. Tooth mobility: By the back of the mirror checked by the assessor to detect mobility in any direction

This assessment will be conducted every follow-up visit throughout the study period at baseline, 6, 12 and 18 months.

Secondary outcome

Radiographic assessment to detect stage of root development and presence of radiolucency through standardized periapical radiograph by parallel technique using film holder. This assessment will be conducted every follow-up visit throughout the study period at baseline, 6, 12 and 18 months.

Postoperative records will be performed by the assessor to avoid individual variability and to promote data quality.

19- Data management:

Explanation to the parents about the importance of the follow-up visits in addition to treatment of other dental problems are plans to promotes participants retention and complete the follow-up.

Also, phone calls before the dates before the next follow-up visit will be scheduled.

All findings will be documented in the examination sheet then transferred electronically to computer in secured lace sequentially.

20- statistical methods:

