All data will be collected, checked, revised, tabulated and entered into the computer. Qualitative data will be presented as frequencies and percentages. Quantitative data will be presented as mean and standard deviation values. Chi-square test and Fisher's Exact test will be used for comparisons regarding qualitative data. Student's t-test will be used to compare between mean age values in the two groups. Friedman's test will be used to study the changes by time within each group. Kaplan-Meier survival curve will be constructed to calculate the mean survival estimates of the two groups. Comparison between survival times will be performed using Log rank test.

The significance level will be set at $P \leq 0.05$. Statistical analysis will be performed with IBM® SPSS® Statistics Version 20 for Windows.

21-Monitoring:

The study data and results will be monitored regularly by the assessor who will have full access to these data.

22- Harms:

No reported adverse effects for both testing pulpotomy agents. Any adverse events appear during the trial will be recorded, documented and treated.

23-Auditing:

Auditing of the study design will be done by the evidence-based committee, Faculty of Dentistry -Cairo University.

V- Ethics and dissemination:

24-Research ethics approval:

This protocol and the template informed consent form will be reviewed by the Ethics Committee of Scientific Research - Faculty of Oral and Dental Medicine - Cairo University.

25-Protocol amendments:

Any modification to the protocol which may have an impact on the conduction of the study, potential benefit of the patient or my affect patient safety including, the changes of study objectives, study design, sample size or significant administrative aspects will require a formal amendment to the protocol.

26-Consent and Assent:

Researcher will discuss the trial with legal guardian of each participating child. They will be able to have an informed discussion with the researcher after explaining the procedure in simple words. Verbal assent will be taken orally from the participating child while written consent will be taken from the legal guardian of each participating child who is willing to participate in the trial. All consent forms will be translated into Arabic.

27-confidentiality:

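### Nothing collects symptoms or treatment between the 6-monthly visits, so early or resolved events may be missed and the promise to record adverse events has no method behind it

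*Combined protocol and SAP*

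**What the plan says.** **Pain.** Section 18 (Data collection methods) describes the item as "postoperative pain: through asking the child and the parent if there is pain", and continues "either continuous or intermittent". The outcome table in Section 12 names a pain questionnaire as the tool; neither its items nor its recall window is given.

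**Signs.** The other clinical components are examined, for example "Swelling: through visual examination by the assessor either intraorally or extra-orally". Sinus tract and mobility are handled in the same way.

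**Timing.** "This assessment will be conducted every follow-up visit throughout the study period at baseline, 6, 12 and 18 months". The timeline in Section 13 has no post-operative assessment before 6 months.

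**Contact outside the visits.** Section 19 (Data management) says that "phone calls before the dates before the next follow-up visit will be scheduled". This stands among the measures to keep families in the study, and no symptom question is attached to it.

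**Failed teeth.** Section IV, on discontinuing or modifying the intervention, says: "In case of an unsuccessful outcome after pulpotomy, the teeth will be managed by other pulp therapy techniques". How such a tooth is scored or dated afterwards is not stated.

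**Harms.** Section 22: "Any adverse events appear during the trial will be recorded, documented and treated". No form, question or schedule is given.

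**Analysis.** Section 20 plans Kaplan-Meier curves, mean survival estimates and a log-rank test, without defining the event or its date.

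**The concern.** An examination shows what is there on the day. A present-tense pain question with no recall window may be answered in the same way. Take a child with pain and swelling in month 2 that settles, or is treated at another clinic. At month 6 the child can answer no to pain and look normal on the clinical signs, and no written procedure would bring the earlier episode into the record.

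Three things are at stake:

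- **Clinical success.** Missed failures raise apparent success. If they are missed at the same rate in both arms, the difference between arms shrinks.
- **Time to failure.** A failure found at a visit arose at some point in the preceding 6 months.
- **Harms.** The first half-year after the procedure has no planned symptom enquiry, in children aged 7.5 to 9.

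**Working it through.** **1. What each section would catch, for an event that begins and ends between two visits**

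| Section | What it provides | Catches the event? |
|---|---|---|
| 13, timeline | Clinical and radiographic assessment at 6, 12 and 18 months | Only if signs persist or leave a trace |
| 18, pain | Question about whether there is pain, continuous or intermittent | Depends on a recall period that is not stated |
| 18, swelling, sinus, mobility | Examination at the visit | No, if resolved |
| 19, phone calls | Calls before visits, listed with retention measures | No symptom question described |
| IV, unsuccessful outcome | Further pulp treatment | No scoring or dating rule |
| 22, harms | Undertaking to record adverse events | No method given |

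No row supplies a procedure for events between visits.

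**2. Dating of failures.** Consecutive assessments are 6 months apart (0, 6, 12, 18). A failure first seen at visit t arose between t − 6 and t months. Entering the visit date lengthens the recorded time by 0 to 6 months, unless an unscheduled attendance supplies a date.

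**3. The plan's own sample size.** Inputs from Section 14: success 90% (MTA) and 50% (Biodentine, assumed), alpha 0.05, power 80%. I take the test as two-sided, which the plan does not state.

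n per arm = [1.96 × √(2 × 0.70 × 0.30) + 0.84 × √(0.90 × 0.10 + 0.50 × 0.50)]² ÷ 0.40² ≈ 19.4, rounded up to 20.

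This matches the stated 20 per group. Normal-approximation power at 20 per group is 81%. The sample-size arithmetic is not in question here.

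**4. Illustration of missed failures.** Assumption, not in the documents: a share h of failures goes unrecorded, the same h in both arms.

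- Observed MTA success = 1 − 0.10 × (1 − h)
- Observed Biodentine success = 1 − 0.50 × (1 − h)
- Observed difference = (1 − h) × 40 points

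| h | MTA | Biodentine | Difference | Power at 20 per group |
|---|---|---|---|---|
| 0 | 90% | 50% | 40 points | 81% |
| 10% | 91% | 55% | 36 points | 75% |
| 25% | 92.5% | 62.5% | 30 points | 63% |
| 50% | 95% | 75% | 20 points | 42% |

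On the 20 per group planned for analysis, the Biodentine arm would have 0.50 × 20 = 10 failures. At h = 25%, 2.5 of them would be entered as successes.

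**The case against.** The text is less restrictive than it may first appear, and four stronger readings do not hold.

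- **Pain counted only on the visit day.** A reader might infer this, but the item covers intermittent pain and a questionnaire of unstated content is named. The recall window is undefined; it is not fixed at one day. Even so, an episode that ended months earlier is not current intermittent pain, and an unspecified questionnaire cannot be assumed to ask about it.
- **No contact for 6 months.** Calls precede the visits, and treatment of other dental problems may bring children back. What falls at 6 months is the first planned outcome assessment.
- **Treated events scored as absent.** No rule says so. An unsuccessful outcome is a recognised state, and a survival analysis normally keeps a recorded failure as a failure. The radiographs at 6, 12 and 18 months might also reveal treatment elsewhere or a failing pulp, although they belong to the secondary outcome. The gap is a missing rule.
- **Section 22 impossible to fulfil.** It is not limited to scheduled visits, so parent reports or unscheduled attendance could satisfy it. The method is unstated.

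The illustration is also open to challenge. No figure in the documents supports any value of h, equality between arms is assumed, and the 50% rate is itself a planning assumption. For a cumulative outcome, a failure is lost only if it is missed at every later visit too.

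Finally, one might wish to count every recalled symptom as a primary failure. That would redefine the outcome and rest it on up to 6 months' recall. Antibiotic use and dental treatment also match no listed primary component. This objection stands, and the fix below respects it.

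**Conclusion.** The concern holds as a gap in data collection. Followed as written, the plan may miss early or resolved events and those treated elsewhere. It dates visit-detected failures only to within 6 months, and it gives no means of meeting its own commitment on adverse events. These conclusions follow from the text and need no assumption.

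The size of any bias cannot be derived from the documents. The 36, 30 and 20 points hold only if the stated share of failures is missed equally in both arms and the planning rates of 90% and 50% are true. They show the direction and the lack of margin in a trial planned at 80% power; they do not estimate the loss.

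The gap is worth closing before data collection, because the remedy is cheap and unrecorded events are hard to recover later.

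**What to change.** 1. **Ask about the interval.** At every visit, and in the calls already planned in Section 19, ask whether since the last contact there has been pain, swelling, a gum boil, antibiotic use or dental treatment for this tooth, and when. Add one such call early after treatment. State the recall period of the visit pain item.
2. **Log it.** Enter the answers and any unscheduled attendance, with dates, in the adverse-event log, and refer to that log in Section 22.
3. **Score re-treated teeth.** State in Section 20 that a tooth receiving further pulp treatment is carried forward as a failure dated at that treatment.
4. **Leave the primary outcome as assessed at the visits.** Keep the assessor-observed signs as they are. Report parent-recalled, resolved symptoms separately, and include them in a sensitivity analysis.

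**Cost.** One question on the examination sheet, a short call script, and one extra call per child (2 × 23 = 46 calls). Parent recall is imperfect, which is why recalled symptoms stay outside the primary outcome. No treatment procedure changes.

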Clinical and Radiographic Evaluation of Pulpotomy Technique for Preserving Vitality of Traumatized Anterior Permanent Immature Teeth: A Randomized Clinical Trial

Protocol submitted to the Faculty of Dentistry, Cairo University
by
[name]
Associate Professor of Pediatric Dentistry

Faculty of Dentistry
Cairo University
January 18 , 2017

I. Administrative information:

1. Title:

Clinical and Radiographic Evaluation of Pulpotomy Technique for Preserving Vitality of Traumatized Anterior Permanent Immature Teeth: A Randomized Clinical Trial

2. Protocol Registration:

To be registered on Clinicaltrial.gov

3. Protocol version:

Final version.

4. Funding:

This trial is self-funded.

5. Roles and responsibilities:

1. **[name] ([name])** Associate Professor of Pediatric Dentistry, Cairo University. Responsible for the clinical part of study, and Data monitoring.
2. **[name] ([name])** Professor of Pediatric Dentistry, National University of Singapore, responsible for the writing revision and proof reading.
3. **[name] ([name])** Associate Professor of Pediatric Dentistry, Misr University for sciences and technology. Responsible for the clinical evaluation of the cases at the evaluation intervals

II. Introduction

6-background and rationale:

Description of research question:

P: children with vital traumatized exposed immature maxillary permanent incisors

I: Pulpotomy using Biodentine

C: MTA pulpotomy

O:

	Outcome	Tool/Device	Unit
Primary Outcome	spontaneous pain, sensitivity to percussion/ palpation)	Pain questionnaire	Binary
	Swelling or sinus tract	Visual examination by the third author	Binary
	Mobility	Back of the mirror	Binary
Secondary outcome	Stage of root development	Standardized periapical	4 stages
	Presence of radiolucency	Standardized periapical	Binary

S: Randomized clinical trial

T: 18 months (Baseline, 6, 12 and 18 months)

Research question: is Biodentine used as pulpotomy material in vital traumatized exposed immature maxillary permanent central incisors more successful clinically and radiographically than MTA pulpotomy?

Justification for undertaking the trial:

The occurrence of dental trauma in permanent teeth is a common event worldwide [1]. Children and adolescents are most frequently affected, and two-thirds of all dental trauma are found among these populations [1,2], with the anterior permanent teeth being the most affected [1, 4-6].

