Traumatic injuries affecting teeth may result in pulpal and periapical disease. Complicated crown fractures which involve the enamel, dentin and pulp occur in 0.9 - 13% of all dental injuries [2,3]. Vital pulp therapy (VPT) is the treatment of choice for traumatized immature teeth with pulp exposure [5,6]. VPT aims for continuation of root development, which leads to apical closure and strengthening of the root structure [7]. If the pulp vitality of a traumatized immature tooth is lost,

endodontic treatment will constitute a real challenge. It is difficult to obtain an appropriate apical seal in these teeth by using the conventional obturation methods. Furthermore, thin root canal walls make the teeth susceptible to future fractures [8].

Primary objective of pulp therapy is to maintain the integrity and health of the teeth and their supporting tissues and to preserve vitality of the tooth pulp, especially in young permanent teeth with immature roots, where the pulp is integral to continue apexogenesis. Long term retention of a permanent tooth requires a root with a favorable crown/ root ratio and dentinal walls that are thick enough to withstand normal function. therefore, pulp preservation is a primary goal for treatment of the young permanent dentition. [9]

In modern dentistry, vital pulp therapy (VPT), whenever feasible, should be considered as an effective reasonable alternative to endodontic treatment [10]. In clinical practice, VPT includes stepwise excavation, pulp capping (direct and indirect) and pulpotomy (miniature, partial and complete), based on the amount of preserved coronal pulp [11]. The main goal of these conservative methods is to maintain the normal pulp or remove contaminated pulpal tissue in order to promote the repair process [9-11]. Therefore, immature teeth eventually gain additional benefit from VPT, considering their weak structural nature [11].

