Radiographic imaging of the dentoalveolar complex has been assessed using conventional periapical radiography, the benchmark for intraoral radiographic imaging for decades. Their known limitations of image magnification, distortion, superimposition and overlap of anatomy always led to unclear and misrepresentation of structures. Although the advent of digital intraoral radiography didn’t improve these limitations, it provided a more active image manipulation than the film-based radiographs and reduced patient exposure substantially. [19, 20]

7 - Objectives and hypothesis:

The objective of this prospective randomized clinical trial is to compare the clinical and radiographic outcomes of MTA and Biodentine as vital pulp therapy materials (pulpotomy) preserving the vitality of traumatized immature anterior permanent teeth.

8-Trial Design:

Randomized clinical trial (RCT), parallel groups with 1:1 allocation ratio, Triple blinded (patient, clinical and radiographic assessor of the results and statistician)

III- Methods:

9-Study settings:

This study will be carried out on patients attending the outpatient clinic in Pediatric Dentistry department, Faculty of Dentistry, Cairo University, Egypt. the procedures will be carried out by [name] Associate Professor of Pediatric Dentistry in Pediatric Dentistry clinic. expected time duration from 2017 to 2018.

10- Eligibility criteria:

Inclusion criteria

- The patient age range 7.5-9 years.
- Noncontributory medical history
- Unilateral/ and or bilateral central incisors tooth with complicated trauma (exposure size $\geq 1\text{mm}$)
- The tooth should give positive response to cold testing
- Clinical diagnosis of reversible pulpitis without periapical rarefaction
- The tooth is restorable, mobility was within normal limits
- No signs of pulpal necrosis including sinus tract or swelling

Exclusion criteria

- Teeth with mature roots
- Signs and symptoms of irreversible pulpitis
- Non-restorable teeth
- Negative response to cold testing, the presence of sinus tract or swelling
- No pulp exposure
- Bleeding could not be controlled after full pulpotomy in 6 minutes

IV- Intervention:

Diagnosis:

1. Full history data will be collected, including personal, medical and previous dental data
2. Clinical examination using mirror and probe to assess the inclusion criteria.
3. Radiographic examination using preoperative digital periapical radiograph to assess the inclusion criteria.

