Secondary outcome	Stage of root development	Standardized periapical	4 stages
	Presence of radiolucency	Standardized periapical	Binary

Primary outcome:

Clinical assessment of the findings in the table will be conducted at follow up intervals (baseline, 6, 12 and 18 months)

Secondary outcome:

Radiographic assessment of stage of root development, and presence of radiolucency will be conducted through digital periapical radiographs by parallel technique using film holders. The assessments will be carried out at follow up intervals (baseline, 6, 12 and 18 months)

13- Participants timeline:

	Study period				
	Enrolment	Allocation	Post allocation		Close out
Time point	For 9 months	0	6 months	12 months	18 months
Enrolment:					
Eligibility screen	✓				
Informed consent	✓				
History taking	✓				
Clinical examination	✓				
Preoperative radiograph	✓				
Allocation		✓			
Interventions:					
Access preparation		✓			
Placement of Biodentine (experimental group)		✓			
Placement of MTA (Control group)		✓			
Final restoration		✓			
Assessment					
Periapical radiograph as baseline reference			✓	✓	✓
Clinical examination to assess pain, swelling, fistula, tooth mobility			✓	✓	✓
Periapical radiograph to assess stage of root development and presence of radiolucency			✓	✓	✓

14- Sample size calculation:

Sample size is calculated based upon the results of Alqaderi et al (2014) [21] who reported clinical success rate (primary outcome) for MTA = 90%. Since no relevant literature reported the clinical success rate of Biodentine in permanent teeth of pediatric patients, the success rate was assumed to be 50%. Using alpha level = 0.05 and β level = 0.20 (80% Power); the minimum estimated sample size will be 20 subjects per group for a total of 40 subjects. To compensate for a drop-out rate of 15%, the number is increased to 23 subjects per group for a total of 46 subjects.

Sample size calculation will be performed using IBM® SPSS® Sample Power® Release 3.0.1.

15- Recruitment:

All patients attending the outpatient clinic in pediatric dentistry department complaining from traumatized immature permanent maxillary central incisors will be screened and enrolled in the study if they meet the eligibility criteria.

16- Allocation:

Sequence generation:

Access cavity in traumatized central incisors will be assigned into experimental or control group using simple randomization 1:1 by the help of the computer software(random.org).

Allocation concealment mechanism:

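### Root-development stage is an ordered outcome with a baseline value, but the only between-group test the plan offers for it uses neither

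*Combined protocol and SAP*

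**What the plan says.** Section 12 lists stage of root development, on four stages, as a secondary outcome beside presence of radiolucency. Section 18 describes the measurement as "Radiographic assessment to detect stage of root development and presence of radiolucency through standardized periapical radiograph by parallel technique using film holder", at baseline and at 6, 12 and 18 months. A baseline film exists in any case, because the Diagnosis steps include "Radiographic examination using preoperative digital periapical radiograph to assess the inclusion criteria".

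Section 20 does not mention root stage. For categorical data it says "Chi-square test and Fisher's Exact test will be used for comparisons regarding qualitative data". For repeated visits it says "Friedman's test will be used to study the changes by time within each group". The t-test is confined to age, and the log-rank test to survival times. The plan names no rank, trend or ordinal test, no baseline adjustment and no visit for the between-group comparison.

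**The concern.** The protocol's rationale is that "VPT aims for continuation of root development, which leads to apical closure and strengthening of the root structure", and its research question is whether Biodentine is "more successful clinically and radiographically than MTA pulpotomy". If one material does better on this outcome, its roots should be further along the scale, which is an ordered difference. A chi-square or Fisher test on a 2×4 table gives the same p-value if the four stage labels are shuffled, so it spends power on patterns that are not of interest. It also ignores where each root started.

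Friedman's test does use order and the repeated visits, but only inside each arm. A change over time in one arm and not in the other is not a comparison of the materials.

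What is at stake is a greater chance of missing a real difference on a secondary outcome. The type I error of the planned test is sound when each child gives one tooth. With three follow-up visits and none named, the visit could also be chosen after the data are seen.

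**Working it through.** **1. What the plan's own figure covers.** Section 14 uses 90% against 50% clinical success, α = 0.05 and 80% power. With pooled variance and a two-sided test:

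n = [1.96·√(2·0.7·0.3) + 0.8416·√(0.9·0.1 + 0.5·0.5)]² / 0.4² = 1.761² / 0.16 = 19.4, so 20 per arm.

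Adding 15% gives 20 × 1.15 = 23, as stated (20 / 0.85 = 23.5, or 24, by division). The figure reproduces, but it concerns clinical success only. Nothing in the plan sizes the comparison of root stage.

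**2. Which section 20 method can compare stage between arms.**

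| Method | Scope in section 20 | Compares stage between materials? |
|---|---|---|
| Student's t | mean age | no |
| Friedman | change within each group | no |
| Kaplan-Meier, log-rank | survival times | no |
| Chi-square, Fisher | qualitative data | yes, the only one left |

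**3. Simulation inputs.** The documents give no stage distribution, effect size or correlation with baseline, so these are assumptions: 20 evaluable children per arm, one tooth each, and a normal latent scale with follow-up = r·baseline + √(1−r²)·error + δ·arm. Baseline is cut into three equal immature stages. Follow-up is cut into four stages, either equal in the reference arm or 2/6/22/70% (a ceiling). α is 0.05 and each row has 10,000 trials. Expected counts were too small for chi-square (more than 20% of cells below 5) in 98–100% of trials, so Fisher is the relevant default.

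| Stages | δ (SD) | r | Fisher | Rank-sum | Rank ANCOVA |
|---|---|---|---|---|---|
| Equal | 0.6 | 0.3 | 26.0% | 39.8% | 41.6% |
| Equal | 0.6 | 0.7 | 25.9% | 40.1% | 55.7% |
| Equal | 0.8 | 0.3 | 43.5% | 60.8% | 62.6% |
| Equal | 0.8 | 0.7 | 43.0% | 61.6% | 79.1% |
| Ceiling, other arm higher | 0.6 | 0.3 | 15.8% | 25.9% | 26.5% |
| Ceiling, other arm higher | 0.6 | 0.7 | 16.1% | 26.4% | 31.2% |
| Ceiling, other arm higher | 0.8 | 0.3 | 25.6% | 39.4% | 39.8% |
| Ceiling, other arm higher | 0.8 | 0.7 | 25.1% | 38.7% | 44.5% |
| Ceiling, other arm lower | 0.8 | 0.3 | 40.1% | 56.8% | 58.2% |
| Ceiling, other arm lower | 0.8 | 0.7 | 39.3% | 56.4% | 71.3% |

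**4. Gain from order (rank-sum minus Fisher).** Equal stages: 39.8 − 26.0 = 13.8 up to 61.6 − 43.0 = 18.6 points. Ceiling, other arm higher: 25.9 − 15.8 = 10.1 up to 39.4 − 25.6 = 13.8. Ceiling, other arm lower: about 17.

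**5. Gain from baseline (rank ANCOVA minus rank-sum).** At r = 0.3: 0.4 to 1.8 points. At r = 0.7: 26.4 to 31.2 (4.8) up to 61.6 to 79.1 (17.5). Excluding mature roots may narrow the baseline range. At r = 0.7 and 0.8 SD, a 15/70/15% baseline gives 60.6 to 73.9% (equal) and 39.7 to 44.9% (ceiling). An 80/20% baseline gives 60.9 to 68.5% and 38.9 to 41.0%.

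**6. False positives.** With no effect, rejection was 4.4–5.2% for all tests with equal stages. At the ceiling it was 3.9–4.1% for Fisher and 4.6–5.2% for the rank tests. The extra power does not come from an inflated error rate.

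**7. A different model.** This run used proportional odds, control stages of 15/25/30/30%, a 35/40/25% baseline and chi-square as the comparator.

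| Odds ratio | Baseline correlation | Chi-square | Rank-sum | Rank ANCOVA |
|---|---|---|---|---|
| 3 | 0 | 29% | 45% | 44% |
| 3 | 0.4 | 23% | 38% | 42% |
| 3 | 0.65 | 15% | 26% | 39% |
| 5 | 0 | 55% | 75% | 73% |
| 5 | 0.4 | 46% | 65% | 71% |
| 5 | 0.65 | 28% | 44% | 66% |
| 8 | 0.65 | 47% | 68% | 85% |

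Order is worth about 11 to 21 points here. At odds ratio 5 and correlation 0.4, chi-square needs roughly 28–32 per arm (62% at 28, 71% at 32) to match the rank test's 65% at 20.

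**8. Where the gain fails.** At 0.3 SD every test had only 7–19% power. With a non-monotone difference (one arm more spread out), chi-square had 48% power and the rank test 7%.

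**The case against.** - **The premise is inferred.** Section 20 never assigns a test to root stage. That is true, but no other listed between-group method fits. If stage was not meant to fall under qualitative data, the plan has no between-group test for it, and the same edit is needed.
- **The scale is undefined.** The documents give four stages without defining them. An ordered analysis needs the definitions and their order in writing, so this belongs in the fix.
- **Failed teeth.** The Intervention section sends unsuccessful teeth to other pulp therapy, after which 18-month stage no longer reflects the allocated material alone. On the planning rates that is 20 × 0.10 = 2 against 20 × 0.50 = 10 teeth. If they were excluded (18 against 10, an assumption), rank ANCOVA power fell to 28–36% (equal stages, 0.6 SD), 45–58% (equal, 0.8 SD) and 13–25% (ceiling). The rank-sum advantage over Fisher was still about 10–21 points in that run. The absolute powers above are therefore optimistic, and excluding such teeth could itself bias the comparison. This problem affects any test and does not favour Fisher.
- **Direction.** A rank test loses badly if the arms differ in spread and not in level. This stands. It is a reason to show the counts at each stage, but the research question itself is directional.
- **Too much machinery for 46 children.** Partly fair. One named test, the counts and one effect estimate are enough.

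**Conclusion.** The concern holds, as a point to consider and with medium confidence in its size. The planned default leaves out stage order and a baseline measurement already scheduled. For a mainly one-directional shift of 0.6–0.8 SD at 20 evaluable per arm, ignoring order costs about 14–19 power points with evenly spread stages, about 10–14 at the ceiling with the other arm higher, and about 17 with it lower. The baseline part is worth little if starting stage predicts follow-up weakly, and up to 18 points if it predicts strongly.

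These sizes rest wholly on assumed inputs. The direction of the order effect was the same under two different models. The loss is one of efficiency on a secondary outcome; the primary analysis and N = 46 do not change. Power reaches about 80% only in the most favourable scenarios (79% at 0.8 SD, and 85% at an odds ratio of 8, both with strong baseline correlation). A non-significant result on root stage will therefore usually be inconclusive whichever test is used.

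**What to change.** Define the four stages and their order in section 12, and add to section 20:

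> Stage of root development at 18 months will be compared between groups by rank analysis of covariance adjusted for baseline stage (preoperative radiograph), with child-clustered standard errors if a child contributes two teeth. Counts at each stage will be shown by group. A proportional-odds odds ratio with 95% confidence interval will be reported where it can be estimated. Friedman tests are descriptive. Chi-square and Fisher tests apply to the binary outcomes.

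Also state how teeth given another pulp treatment before 18 months are counted.

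The clustering clause is there because eligibility admits "Unilateral/ and or bilateral central incisors tooth with complicated trauma". In an assumed check (40 children, 10–50% with two teeth in the same arm, within-child correlation 0.5–0.8), tooth-level Fisher error was 4.4–11.4%, against 5.1–6.5% for the clustered rank analysis. The check did not cover two teeth in opposite arms.

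A Wilcoxon test stratified by baseline stage is an acceptable alternative, with 0–3 points less power than rank ANCOVA. At r = 0.3 it is no better than the plain rank-sum test (for example 59.9% against 60.8%). Name one method before data are seen.

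Cost: a few sentences and slightly more analysis work, with no added patients, visits or radiographs. Confirm that the named software can run the clustered version. A rank-scale effect is harder to interpret. With the ceiling distribution and the other arm higher, the odds ratio has no finite estimate in about 6–7% of trials at 0.6 SD and 14–15% at 0.8 SD.
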